8.0 AGENT INFORMATION

8.1 8-Chloro-adenosine

8.1.1 Description and classification

Chemical Name: 8-chloro-adenosine

Other name: NSC 354258

Manufacturer: Active Pharmaceutical Ingredient produced by Ash Stevens. Drug formulation manufactured by the University of Iowa Pharmaceuticals.

8-chloro-adenosine is an adenosine analogue with a ribose sugar and a chlorine group at the 8-position of the adenine base. 8-chloro-adenosine has a molecular formula C₁₀H₁₂N₅O₄Cl and molecular weight of 301.68. The melting point is 198-199°C. It is a white powder that has an intrinsic solubility in water of 4.8 mg/ml. It is stable (no degradation) at 25°C or 35°C for at least 2 months, however, it is unstable in water at pH<3 and pH>8. A 5 mg/ml aqueous solution appears to be stable at pH 7.0 for over 1 year.

8-chloro-adenosine was prepared in a 3-step reaction from adenosine: 1) acetylation of adenosine with acetic anhydride; 2) reaction with m-chloro-phenylbenzoic acid/HCl to yield 8-chloro-adenosine triacetate; 3) deacetylation with sodium methoxide/methanol.

The drug is supplied at a concentration of 5 mg/mL in 5% dextrose (20 mL per vial).

8.1.2 Mode of action, pharmacology, toxicology

See Section 2.4.2 for mechanism of action, Sections 2.5 and 2.6 for toxicology, and Section 2.6 for pharmacology.

8.1.3 Storage and stability

Stability testing will be ongoing by the City of Hope Manufacturing Core. The aqueous solution should be maintained at room temperature.

8.1.4 Preparation

Agent preparation will proceed as follows:

- Calculate dose based on assigned dose level and patient's BSA using the body weight obtained on Day 1 of treatment cycle.
- Check vial for particulates. Do not use if there is evidence of particulates.
- Withdraw the calculated dose volume of 8-chloro-adenosine.
- Inject calculated dose via a 0.22 μ m filter into 5% dextrose to a concentration not exceeding 2 mg/ml.
- Store prepared agent at room temperature until infusion.

Note: Infusion should be completed within 12 hours of preparation.

8.1.5 Agent administration

8-chloro-adenosine will be infused over 4 hours +/- 10 minutes. The infusion rate should not exceed 500 ml/hr.

Infusion is to be completed within 12 hours of agent preparation.

8.1.6 Accountability

The investigator, or a responsible party designated by the investigator, must maintain a careful record of the inventory and disposition of each of the agents using the NCI Drug Accountability Record or another comparable drug accountability form.

9.0 CORRELATIVE/SPECIAL STUDIES

9.1 Pharmacokinetics and Pharmacodynamics

9.1.1 Clinical Pharmacology Objectives

- To describe the plasma, urinary and cellular pharmacokinetics of 8-chloro-adenosine and metabolites.
- To determine the impact of 8-chloro-adenosine on cellular ATP pool in AML blasts.
- To assess the impact of 8-chloro-adenosine therapy on select short-lived mRNAs and corresponding proteins in circulating AML blasts.
- To correlate clinical responses and toxicity with plasma/urine 8-chloro-adenosine level (PK), cellular 8-Cl-ATP (PK) and cellular ATP pool.

9.1.2 Blood Sample Collection

Blood samples will be collected from an indwelling venous catheter or by venipuncture, at a **separate anatomic** site as drug infusion e.g., in the opposite arm of the drug infusion. In cases of poor venous access, specimen may be drawn from a catheter lumen separate from that used for drug infusion after approval by PI. At each time point indicated in Table 9.1.2, peripheral blood will be collected into **three*** **7 ml green-top tubes** (sodium or lithium heparin) containing deoxycoformycin to prevent blood clotting and ex vivo deamination of 8-chloro-adenosine. Only one 7ml green top tube need be collected unless circulating blast count is over 5000/ μ L. Tubes will be **inverted several times** and then **immediately placed on ice** and brought **promptly** (so that the sample can be processed within the hour) to the CICSL (Shapiro rm. 1042) or other processing laboratory. Notify the CICSL ([name] or her representative) by e-mail to [contact] in advance of sampling (ideally >1 day in advance).

Table 9.1.2 Time Points of Blood Sample Collection for PK/PD Studies

Pt. MRN:	Pt. Initials (F, M, L):	Pt. Study ID:
----------	-------------------------	---------------

	Time Point During Cycle 1	No. of tubes collected*	Time (h:m of 24-hr clock)	Date	Initials
Day 1	0-24hr Pre-infusion				
	Start of Infusion TIME	--			
	Within last 15 minutes of infusion				
	End of Infusion (EOI) TIME#	--			
	1 hr post EOI +/- 15 min				
	3 hr post EOI +/- 15 min				
	6-8 hr post EOI				
Day 2	12-18 hr post EOI				
	0-1 hr pre-infusion				
	Start of Infusion TIME	--			
	Within last 15 minutes of infusion				
Day 3	End of Infusion TIME#	--			
	0-1 hr pre-infusion				
	Start of Infusion TIME	--			
	Within last 15 minutes of infusion				
Day 4	End of Infusion TIME#	--			
	0-1hr Pre-infusion				
	Start of Infusion TIME	--			
	Within last 15 minutes of infusion				
Day 5	End of Infusion TIME#	--			
	0-1hr Pre-infusion				
	Start of Infusion TIME	--			
	Within last 15 minutes of infusion				
	End of Infusion TIME#	--			

*Collect **three tubes** if patient has \geq 5000 circulating leukemic blasts per micro liter of blood (on a recent clinical lab result (e.g. within 24 hours) and if collection occurs when cell processing is available by CICSL. Otherwise collect only **one tube** and process sample for plasma only (may be done by Clinical Pathology Lab if CICSL not available).

End of infusion time includes flush time.

The biospecimen coordinator for the study can be reached at [contact] [name].

9.1.3 Urine Specimen Collection

All urine will be collected in three 8 hr +/-30 min sequential intervals (e.g. 0-8 hrs, 8-16 hrs, and 16-24 hrs) during the first 24 hours after the first dose of cycle 1. Samples will be delivered to CICSL in Shapiro room 1042 at room temperature. Samples may be delivered to CICSL in a single batch.

9.1.4 Sample Processing

Urine

- For urine samples, the total volume will be recorded for each of the 3 collection intervals (0-8 hrs, 8-16 hrs, and 16-24 hrs) and a 10 ml aliquot for each of the three time-points will be stored frozen at < -70°C until shipping.

Plasma

- Sample processing is to start within 1 hour of sample collection.
- For plasma, anti-coagulated whole blood samples (one 7 ml green-top tube) will be processed by centrifugation for 10 minutes at 1500 x g at 4°C. The resulting plasma will be transferred to appropriately labeled polypropylene tubes and frozen at < -70°C until shipping.

PBMCs

- Sample processing is to start within 1 hour of sample collection.
- For leukemic blast isolation, blood samples will be collected from those patients with \geq 5000 circulating leukemic blasts per microliter of blood and at times when laboratory processing is available. Peripheral blood mononuclear cells (PBMC) will be isolated from whole blood by Ficoll-gradient separation as described:
 - Whole blood (two 7 ml green-top tubes) will be diluted 1:5 with ice cold PBS and carefully layered on top of 10 ml of Histopaque® (Sigma cat. # 1077-1) in 50 ml polypropylene centrifuge tubes.
 - Blood/ficoll tubes will then be centrifuged at 1500 x g for 25 minutes and 4°C with the break in the “off” position. The mononuclear blood cells at the interface between the Histopaque® and the top aqueous layer will be aspirated into a clean 15 ml polypropylene centrifuge tube using a glass Pasteur pipette.
 - The aspirated PBMC will then be washed x 2 in ice cold PBS, cells will be counted, and then divided to perform pharmacodynamic studies and correlative studies as indicated in the table below. In case of limited cell number, PBMC samples for intracellular PK will have the highest priority, followed by mRNA measurements, and then RPPA analyses.
- See Table 9.1.4 for allocation of cells by collection time point.
- For intracellular PK measurements, without delay, PBMC cell pellets will be extracted using perchloric acid (Appendix B) and extracts will be stored frozen at < -70°C prior to shipping.
- For mRNA and RPPA measurements, the washed PBMC pellets will be stored frozen at < -70°C pellets prior to shipping.

Table 9.1.4 Allocation of Cells for PK/PD Analysis

	Time Point	Intracellular PK	Cell number	mRNA analysis	Cell number	RPPA + Immunoblot	Cell number
Day 1	Pretreatment	X	1×10^7	X	1×10^7	X	1.5×10^7
	Last 15 min of infusion	X	1×10^7				
	1 hr post EOI	X	1×10^7				
	3 hr post EOI	X	1×10^7	X	1×10^7	X	1.5×10^7
	6-8 hr post EOI	X	1×10^7				
	12-18 hr post EOI	X	1×10^7				
Day 2	Pre-infusion	X	1×10^7	X	1×10^7	X	1.5×10^7
	Last 15 min of infusion	X	1×10^7				

Day 3	Pre-infusion	X	1×10^7				
	Last 15 min of infusion	X	1×10^7				
Day 4	Pre-infusion	X	1×10^7				
	Last 15 min of infusion	X	1×10^7				
Day 5	Pre-infusion	X	1×10^7	X	1×10^7	X	1.5×10^7
	Last 15 min of infusion	X	1×10^7				

9.1.6 Pharmacokinetic Analytic Method

For analysis of human plasma, urine, and cellular samples, a sensitive and selective LC/MS/MS method has been developed and validated at the core facility at MD Anderson to measure primary and active drugs, 8-chloro-adenosine (8-Cl-Ado) and 8-chloro-adenosine triphosphate (8-Cl-ATP), as well as the inactive metabolites 8-chloro-adenine (8-Cl-Ade) and 8-chloro-inosine (8-Cl-Ino).

9.1.7 Pharmacokinetic Data Analysis Methods

Plasma, cellular, and urinary PK data will be analyzed using both non-compartmental and compartmental methods. Non-compartmental PK parameters (e.g. C_{max} , C_{trough} , AUC_{0-t} , CL/F , mean residence time) for 8-chloro-adenosine and its metabolites will be determined using statistical moment theory according to the rule of linear trapezoids. Compartmental PK analyses of the 8-Chloro-adenosine and metabolite data will be performed in ADAPT II software (USC Biomedical Simulations Resource, Los Angeles CA), and secondary PK parameters (e.g. CL_{sys} , V_d , $t_{1/2}$, $AUC_{0-\infty}$) will be determined for each individual. Finally, summary statistics of the individual non-compartmental and compartmental PK parameters will be derived, and the population PK of 8-chloro-adenosine will be described using a two-stage approach.

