5.5 Agent Administration

8-Chloro-adenosine will be administered as an intravenous infusion daily for the first 5 days of each cycle, based on the BSA calculated from the weight measurement taken on Day 1 of the treatment cycle. See Section 8.1.4 for agent preparation. 8-chloro-adenosine will be infused over 4 hours +/- 10 minutes. The infusion rate should not exceed 500 ml/hr. Infusion line will be flushed with 5% dextrose after completion of infusion. Infusion is to be completed within 12 hours of agent preparation during which time it should be stored at room temperature.

Start of cycle criteria are listed in Section 6.2.

Dose levels for dose modification are detailed in Table 5.3.1. There will be no intra-patient dose escalation; participants will undergo dose modification due to toxicity per Section 6.3.2.

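### If the parent drug's plasma half-life is about 1 hour or less, the linear-trapezoid AUC understates exposure and overstates clearance, because the 4-hour infusion is sampled only at its end

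*Combined protocol and SAP*

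**What the plan says.** Section 9.1.7 plans two analyses. Non-compartmental parameters (Cmax, Ctrough, AUC0-t, CL/F and mean residence time are the examples given) "for 8-chloro-adenosine and its metabolites" "will be determined using statistical moment theory according to the rule of linear trapezoids". A compartmental fit in ADAPT II gives systemic clearance, volume, half-life and AUC to infinity for each patient. Both sets are to be summarised, and the section does not say which is preferred where they differ.

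Section 5.5 sets the infusion: "8-chloro-adenosine will be infused over 4 hours +/- 10 minutes". Section 8.1.5 repeats it.

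Table 9.1.2 in section 9.1.2 lists the Day 1 draws of Cycle 1. The baseline draw is "0-24hr Pre-infusion". The next is "Within last 15 minutes of infusion". Then come "1 hr post EOI +/- 15 min", "3 hr post EOI +/- 15 min", one at 6 to 8 h and one at "12-18 hr post EOI". On Days 2 to 5 there is one draw before and one at the end of each infusion. No day has a draw in the first 3 h 45 min of a nominal 4-hour infusion.

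**The concern.** During a constant-rate infusion the plasma level of a rapidly eliminated drug climbs steeply and then levels off near steady state. The linear rule joins zero at the start to the level near the end with one straight line, which lies under that curve for almost 4 hours. The faster the elimination, the larger the share of total exposure that falls in those hours. After the infusion the linear rule errs the other way, because it overstates a convex decline, but that offsets the loss only in part when the half-life is short.

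Describing plasma pharmacokinetics is a stated objective (section 1.3). If elimination is fast, the reported CL/F would be too high and would disagree systematically with the compartmental clearance in the same patients. The error depends on each patient's half-life, so it is not a constant factor that cancels between patients.

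**Working it through.** The plan states no AUC, clearance or half-life in the available text, so there is no figure of its own to reproduce. The check compares the trapezoid sum at the planned times with the exact integral.

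**Inputs from the documents.** Infusion length T = 4 h (section 5.5). Day 1 times from Table 9.1.2, with windows taken at their midpoints: 0, 3.875, 5, 7, 11 and 19 h from the start of infusion.

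**Assumptions.** One compartment, zero concentration before the first dose, and half-life varied from 0.25 to 3 h.

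**Formulas**, in units of the steady-state level Css, with k = ln 2 / half-life:

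- during infusion, C(t) = 1 − exp(−kt)
- afterwards, C(t) = (1 − exp(−kT)) exp(−k(t − T))
- true AUC over the infusion = T − (1 − exp(−kT))/k
- true AUC from 4 to 19 h = (1 − exp(−kT))(1 − exp(−15k))/k
- clearance = dose/AUC, so its relative error is (true AUC / trapezoid AUC) − 1

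**Worked case, half-life 1 h (k = 0.693).** The levels at the six times are 0, 0.932, 0.469, 0.117, 0.007 and 0.000. The trapezoids are:

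- 0 to 3.875 h: 0.932/2 × 3.875 = 1.805
- 3.875 to 5 h: (0.932 + 0.469)/2 × 1.125 = 0.788
- 5 to 7 h: (0.469 + 0.117)/2 × 2 = 0.586
- 7 to 11 h: (0.117 + 0.007)/2 × 4 = 0.249
- 11 to 19 h: 0.007/2 × 8 = 0.029

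Before rounding, the sum is 3.458. The true value is 2.647 + 1.352 = 4.000. The ratio is 0.864, and clearance is 1/0.864 − 1 = 16% too high.

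To see where the loss arises, put the in-infusion sample exactly at the end of infusion. The infusion segment is then 0.9375/2 × 4 = 1.875 against a true 2.647. The post-infusion segments give 1.568 against 1.353. The gain of 0.215 recovers only part of the loss of 0.772.

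**Range of half-lives, nominal times**

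| Half-life (h) | True AUC 0–19 h | Trapezoid AUC | Ratio | Clearance error |
|---|---|---|---|---|
| 0.25 | 4.000 | 2.598 | 0.650 | +54% |
| 0.5 | 4.000 | 2.925 | 0.731 | +37% |
| 1 | 4.000 | 3.458 | 0.864 | +16% |
| 2 | 3.988 | 3.886 | 0.974 | +3% |
| 3 | 3.918 | 3.925 | 1.002 | about 0 |

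**Sampling windows.** Over the draw times that Table 9.1.2 allows, the AUC error is −36.3% to −33.0% at 0.25 h, −27.8% to −24.5% at 0.5 h, −15.1% to −10.8% at 1 h, and −4.4% to +2.1% at 2 h. The windows do not remove the bias at 1 h or below.

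**Two-phase profiles.** With a fast half-life of 0.25 h, a slow one of 2 h and 70% of exposure in the fast phase, trapezoid AUC is about 75% of true. With 0.25 h, 4 h and 30%, it is about 90%. Across the assumed profiles with a fast phase of 0.25 to 0.5 h, the range is roughly 75% to 96%.

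**Check of the alternative integration.** Replace the infusion segment by the integral of Cend(1 − exp(−kt))/(1 − exp(−kT)), which is Cend[T/(1 − exp(−kT)) − 1/k], and use the log-linear rule afterwards. For the 1 h case, take the last in-infusion sample as Cend at 4 h. Then k = ln(0.932/0.469)/1 = 0.687, the infusion part is 2.626 and the rest is 1.350. The total is 3.976, or 99% of true. Over the one- and two-phase cases tried, with k from the end-of-infusion to 1-h decline, recovery was about 97% to 101%.

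**The case against.** The strongest reply is that section 9.1.7 already plans a compartmental analysis. A fit that models the infusion input has no trapezoid error, and nothing in the plan makes the trapezoid AUC the leading figure. This stands as mitigation. It does not stop the biased CL/F from being summarised beside the compartmental clearance with no rule for choosing between them.

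The second reply is that the half-life is unknown. Some of the document was not available for this review, so the absence of a half-life from the visible text does not show that the protocol lacks one. No visible passage places the drug in the affected range, and the largest errors need a single-phase half-life of 0.5 h or less. This also stands, and the point is therefore stated as conditional.

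Two stronger readings are tempting, and the documents support neither:

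- A reader might infer that biased AUC and clearance feed the planned correlation with response and toxicity. The objective in sections 1.3 and 9.1.1 names the plasma or urine drug level, cellular 8-Cl-ATP and the cellular ATP pool. It does not name AUC or clearance.
- A reader might infer that comparison with 1-hour infusion data would show a false fall in exposure, since section 2.3 still describes a 1-hour infusion and the same relative sampling times with a 1-hour infusion give AUC ratios of 1.00 to 1.06. No such comparison is planned. That the draw times were carried over from a 1-hour schedule would also be a guess.

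**Conclusion.** The point holds conditionally. The draw times and the linear rule together understate parent-drug AUC by about 14%, 27% and 35%, and overstate clearance by about 16%, 37% and 54%, at plasma half-lives of 1, 0.5 and 0.25 h. At 2 to 3 h the error is 3% or less at nominal times. These figures rest on a one-compartment model and assumed half-lives; for two-phase elimination the AUC may be anywhere from roughly 75% to 96% of true.

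Mean residence time is derived by the same rule, but its error was not sized here. Measured levels, Cmax and Ctrough do not depend on the rule. The result does not carry over to cellular 8-Cl-ATP, which section 2.6 describes as long-lived, and DLT and response are untouched. This is a cheap improvement to a secondary part of the plan, not a threat to its main conclusions.

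**What to change.** State in section 9.1.7 that, for parent drug in plasma, AUC and clearance are taken from the compartmental fit already planned, with the 4-hour infusion modelled as the input.

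If a non-compartmental value is also reported, integrate the infusion interval as Cend(1 − exp(−kt))/(1 − exp(−kT)) and use the log-linear rule afterwards. Specify that k comes from the decline between the end-of-infusion and 1-h post-infusion samples. In two-phase profiles, k from the 1-h and 3-h samples recovered only about 84% to 95% of true AUC, against about 99% to 101% from the earlier pair.

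Do not change the post-infusion rule alone. Linear-up/log-down on the existing samples enlarges the AUC error to −19.0% at 1 h and −41.5% at 0.25 h, because it removes the partial offset and leaves the infusion segment as it is.

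The cost is wording in the PK analysis; no draw is added. The downside is reliance on a fitted rate constant, or on two draws for k in the non-compartmental version.

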9.1.8 Pharmacodynamic Assay Methods

Measurement of short-lived mRNA transcripts in circulating AML blasts.

Briefly, AML blasts will be washed with cold PBS, pelleted, and frozen at -70°C until transport on dry ice to MD Anderson. Three separate pellets will be needed for mRNA (1×10^7), immunoblot (1×10^7) and RPPA (5×10^6). mRNA transcript levels will be measured using real-time RT-PCR techniques. RNA will be isolated from the cell using Qiagen's Qiashredder and RNAeasy kits using routine methods per the manufacturer's instructions. RNA content will be measured using a NanoDrop2000, then primers and probes for specific transcripts will be used and analyzed on an ABI 7900 (TaqMan) sequence detector.

Measurement of short-lived proteins in circulating AML blasts.

For RPPA analysis, following transport to MD Anderson, the cell pellets will be submitted for the CCG Functional Proteomics Reverse Phase Protein Array (RPPA) Core where the proteins will be extracted and

analyzed on nitrocellulose slides against an extensive set of antibodies. The protein levels will be measured then normalized for protein loading.

9.2 Exploratory Ex-Vivo Molecular Studies

9.2.1 Objectives

- To determine the cytotoxicity of 8-chloro-adenosine toward leukemic progenitor cells in vitro.
- To generate a preliminary pre-treatment RNA/miRNA signature in leukemic progenitor cells, and explore its possible association with in vitro cytotoxicity to 8-chloro-adenosine.
- To explore the possible association between the preliminary RNA/miRNA signature and clinical response to 8-chloro-adenosine.

9.2.2 Bone Marrow and PBMC Collection

When feasible an additional 10 ml of bone marrow will be collected in purple-top (EDTA) tube during pre-study evaluation for correlative studies and at the end of cycle 1 and 2 for future studies. If sufficient bone marrow is not collected, PBMC collected from patients with circulating leukemic blasts (via 26 to 30 ml in purple-top (EDTA) tube) will be obtained for analysis. Samples will be gently inverted to mix the sample and then promptly taken to processing by the biospecimen coordinator designated for this study [contact] [name] and send email to [contact] in advance of sampling (ideally at least a day in advance).

9.2.3 Initial sample processing

Bone marrow will be processed by Ficoll gradient separation as described in Section 9.1.4 to isolate mononuclear cells.

Bone marrow or blood MNC (5x 10e6) will be used for transcriptome analyses.

Cell pellets will be prepared and stored from remaining cells for RT-PCR and immunoblot assays.

9.2.4 In Vitro and Transcriptome Methods

Primary AML cells will be co-cultured in cytokine containing medium with 8-chloro-adenosine for 48 -72 hrs. The proliferation status of co-cultured cells will be evaluated by Ki67 and propidium iodide (PI) labeling and Cell cycle fractions will be analyzed by flow cytometry. Cultured cells will also be labeled with carboxyfluorescein succinimidyl ester (CFSE) to evaluate cell division. Alternatively the proliferation status of the cells will be assessed by MTS assay. We will use Annexin-V and Caspase-3 labeling to detect apoptosis. The differentiation status of co-cultured cells will be evaluated by analysis of CD34, CD33, CD15, CD14 and CD235 expression. Colony forming cells (CFC) will be evaluated in methylcellulose progenitor assays.

In this aim, we hope to find genes and signaling pathways that are correlated with leukemia cells' response to 8-chloro-adenosine. RNA will be extracted from leukemic progenitors for transcription profiling. The isolated RNA will be submitted to the COH Integrative Genomics Core for whole transcriptome analysis using Illumina Hiseq 2500 to profile total cellular RNA (RNA-seq). The core will also assist with data processing across the full data workflow using both commercial and open-source software packages including R/Bioconductor, IGV, Bowtie, TopHat, Cufflinks, Novoalign, Transfac, BWA, GATK, Samtools, Gene Set Enrichment Analysis (GSEA), Ingenuity Pathway Analysis and DAVID.

Transcripts affected by 8-chloro-adenosine will be further validated using real time RT-PCR assay

10.0 STUDY CALENDAR

Table 10 describes required procedures. All procedures may increase in frequency if clinically indicated.

Cycle length will be 28 days (+/-1 day), unless (a) there is a hold in treatment at Day 1, at which time the previous cycle will be extended until treatment is ready to resume on Day 1 of the subsequent cycle or (b) Day 1 assessments have yet to be reviewed for administering Day 1 agent, at which time the previous cycle will be extended until assessments are reviewed.

The day count continues despite a hold or delay in agent administration. Should a hold or delay in treatment occur, evaluations required by the protocol will be conducted at the original times during the cycle, even if agent(s) is not administered.

The Start of Cycle criteria are found in Section 6.2; **Day 1 treatments may not begin until the respective results of the Day 1 procedures are reviewed.** Windows for procedures follow in the table footnotes.

Table 10.0 Study Activity Calendar

	Pre-Study ^a	Cycles 1-4 ^{b,c}					30-day post last dose ^g	Active Follow-up ^h	Survival Follow-up ⁱ
		Day 1 ^d	Day 2-5 ^e	Day 8 ^f	Day 15 ^f	Day 22 ^f			
Informed consent ^j	X								
Medical history ^k	X								
Concurrent meds ^l	X	X		X	X	X	X		
Physical exam	X	X		X	X	X	X		
Vital signs ^m	X	X		X	X	X	X		
ECOG Performance Status ⁿ	X	X					X		
Adverse Event Evaluation ^o			-----X-----				X		
12 lead EKG	X	X ^p	X ^p						
Urinalysis	X	X					X		
B-HCG serum ^q	X								
CBC with diff + platelet count ^r	X	X	X	X	X	X	X		
Chemistry / metabolic panel ^s	X	X	X	X	X	X	X		
Bone Marrow Biopsy	X ^t					X ^{t,u}			
Response Assessment ^v						X ^v		X ^v	
Cardiac monitoring (telemetry unit)		X ^b	X ^b						
8-chloro-adenosine Infusion ^w		X	X						
Research blood collection	XX	X ^y	X ^y						
Research urine collection ^z		X							
Inclusion/Exclusion Criteria ^{aa}	X								
Registration ^{bb}	X								
Other anti-cancer treatment							X ^{cc}	X ^{dd}	
Survival ^{ee}							X	X	

- a. Pre-study procedures to be performed within 14 days of start of treatment.
- b. **Participants will be hospitalized during treatment administration (at minimum during the first six days of the cycle). Patients will undergo continuous cardiac monitoring in telemetry unit from start of treatment until 24 hours after completion of treatment during Cycles 1-4.**
- c. Participants will receive a maximum of 4 study cycles. Participants who experience unacceptable toxicity or disease progression after cycle 2 will forgo additional treatment cycles and proceed to the 30-day-follow-up visit. There will be a +7 day window for start of cycles 2-4.
- d. Day 1 assessments (including EKG) to be performed prior to Day 1 drug. Start of cycle criteria (Section 6.2) must be met before administering Day 1 study agent.

- e. Study agent will be administered daily for five consecutive days. EKG will be performed and reviewed prior to study drug administration. See section 5.2: 'Treatment Cycle Definition' for additional detail regarding treatment administration timing in the event of a hold.
- f. Window for Day 8, 15, and Day 22 assessments is the stated day +/- 2 days. Bone marrow biopsy may be performed between days 22 and 28 after cycle initiation.
- g. Window for the 30-day Post Last Dose visit is +/- 2 days. All participants will be followed until resolution or stabilization of any related serious adverse events occurring during treatment or starting within 30 days of last study drug administration.
- h. Active follow-up will occur for participants who have completed EOT procedures and yet to demonstrate disease progression. The active follow-up visit will take place every 28 days (+/- 5 days) from the day of the EOT Day 30 visit. Active follow-up will continue until an alternative acute leukemia therapy has commenced or until disease progression or up to 2 years following first study agent administration.
- i. Survival follow-up will occur approximately every 3 months (+/- 14 days) from Off-Therapy date for survival status and will occur for up to 2 years following the participant's first study agent administration. Information will be obtained via medical record review, use of the social security registry, or by telephone contact.
- j. Documented informed consent to occur prior to any study related procedures that are not otherwise SOC.
- k. Medical history to include review treatment history for AML, relevant medical history pertaining to study eligibility, and demographic information.
- l. Concurrent medications, supportive care, blood products, or radiation therapy taken or administered during the trial will be documented in the subject's medical record using institutional documentation guidelines. See Section 5.11 for prohibited therapies.
- m. Vital signs: Weight, heart rate, blood pressure, respiration rate, temp. Height required only at baseline.
- n. See Appendix A for ECOG performance status criteria
- o. Adverse events (AEs) experienced by participants will be collected and recorded from signing of informed consent document. AE reporting begins for events that occur after registration. AE recording and reporting will continue until the completion of the Day 30-Post-Last-Dose visit or until resolution or stabilization of any related serious AE occurring before the completion the Day 30-Post-Last-Dose visit, whichever occurs later.
- p. 12 lead EKG to be performed and reviewed within 3 hours prior to study drug administration AND within 1 hour (-5/+10 minutes) post end of infusion.
- q. B-HCG serum pregnancy test for women of childbearing potential only
- r. CBC with differential: erythrocytes (RBC), hemoglobin, hematocrit, platelets, total WBC plus absolute differential counts (neutrophils, lymphocytes, monocytes, eosinophils, basophils).
- s. Serum chemistry panel: Sodium, potassium, chloride, carbon dioxide, creatinine, urea nitrogen, calcium, glucose, albumin, total bilirubin, alkaline phosphatase, total protein, ALG/SGPT, AST/SGOT, LDH, magnesium, phosphorus, and uric acid.
- t. If feasible, from the pre-study, end of cycle 1 and 2 (weeks 4 and 8) bone marrow biopsies, an additional 10 mL will be collected for correlative studies. 10 mL of marrow cells will be collected into a purple top (EDTA) tube, gently agitated, placed on ice and brought promptly (so that the sample

can be processed within the hour) to the [name] in Needleman room 1042. Notify [name] (or his representative) by e-mail to [contact] in advance of sampling (ideally at least a day in advance). NOTE: if the 10ml research bone marrow sample is not feasible for the pre-study bone marrow, blood may be collected as described in footnote 'x'.

- u. Participant will have a bone marrow biopsy after the first and second cycles only (weeks 4 and 8) and when indicated to confirm response. In cases where there is increase of absolute peripheral blood blast count by 50% day 22 bone marrow evaluation can be skipped. For additional correlative sample details see footnote 't' or Section 9.2.2. NOTE: if the 10ml research bone marrow sample is not feasible, blood may be collected as described in footnote 'x'.
- v. Response assessment to use Döhner, 2010 criteria²⁴ detailed in Section 12.2. Response will be assessed at the end of each cycle/just prior to the start of each cycle. While response will be assessed at the end of Cycle 1, the result of the end of Cycle 1 response assessment will not affect whether or not a participant continues onto Cycle 2.
- w. See Section 5.5 for 8-chloro-adenosine administration details. Study agent will be administered daily for five consecutive days, unless there is a hold due to toxicity. See Section 5.2 for administration and day count when there is a hold in agent administration.
- x. For participants who unable to provide the full 10 ml of research bone marrow sample at pre-study (footnotes 't' and 'u'), 26 to 28 ml of peripheral blood will be collected into EDTA purple top tubes. Tubes will be inverted several times and then immediately placed on ice for transportation to [name] in Needleman room 1042. Notify [name] (or his representative) by e-mail to [contact] in advance of sampling (ideally at least a day in advance).
- y. For Cycle 1 only, blood will be collected for PK/PD analysis from a separate anatomic site (e.g. opposite arm) from site drug infusion at various time points. See Section 9.1.2 for details. Notify the CICSL ([name] or her representative) by e-mail to [contact] in advance of sampling (ideally at least a day in advance).
- z. Urine will be collected in 8 hr (+/- 30 min) sequential intervals (e.g. 0-8 hrs, 8-16 hrs, and 16-24 hrs) during the first 24 hours after the first dose of cycle 1. Urine may be maintained at RT, and should be brought to CICSL (Shapiro room 1042). Samples may be delivered to CICSL in a single batch.
 - aa. Inclusion/exclusion criteria are detailed in Section 3.
 - bb. See Section 4.3 for slot reservation and registration process. Registration is to occur prior to start of treatment. Documentation providing Investigator's confirmation that all eligibility criteria are met must be available and provided for registration.
 - cc. Participants will be monitored for anti-cancer treatments during Active Follow-Up. If other anti-cancer treatments (including HCT) are initiated, participants will be removed from Active Follow-Up and proceed to Follow-Up for Survival.
 - dd. Anti-cancer treatments will be collected until the participant completes the study.
 - ee. Survival information and reason for death will be collected until the participant completes the study.

